Appendix A

- /19.18 - (ICD9) HEMARTHROSIS INVOLVING OTHER SPECIFIED SITES
- 719.19 - (ICD9) HEMARTHROSIS INVOLVING MULTIPLE SITES
- I31.2 - (ICD10) Hemopericardium, not elsewhere classified
- I60.00 - (ICD10) Nontraumatic subarachnoid hemorrhage from unspecified carotid siphon and bifurcation
- I60.01 - (ICD10) Nontraumatic subarachnoid hemorrhage from right carotid siphon and bifurcation
- I60.02 - (ICD10) Nontraumatic subarachnoid hemorrhage from left carotid siphon and bifurcation
- I60.10 - (ICD10) Nontraumatic subarachnoid hemorrhage from unspecified middle cerebral artery
- I60.11 - (ICD10) Nontraumatic subarachnoid hemorrhage from right middle cerebral artery
- I60.12 - (ICD10) Nontraumatic subarachnoid hemorrhage from left middle cerebral artery
- I60.2 - (ICD10) Nontraumatic subarachnoid hemorrhage from anterior communicating artery
- I60.30 - (ICD10) Nontraumatic subarachnoid hemorrhage from unspecified posterior communicating artery
- I60.31 - (ICD10) Nontraumatic subarachnoid hemorrhage from right posterior communicating artery
- I60.32 - (ICD10) Nontraumatic subarachnoid hemorrhage from left posterior communicating artery
- I60.4 - (ICD10) Nontraumatic subarachnoid hemorrhage from basilar artery
- I60.50 - (ICD10) Nontraumatic subarachnoid hemorrhage from unspecified vertebral artery
- I60.51 - (ICD10) Nontraumatic subarachnoid hemorrhage from right vertebral artery
- I60.52 - (ICD10) Nontraumatic subarachnoid hemorrhage from left vertebral artery
- I60.6 - (ICD10) Nontraumatic subarachnoid hemorrhage from other intracranial arteries
- I60.7 - (ICD10) Nontraumatic subarachnoid hemorrhage from unspecified intracranial artery
- I60.8 - (ICD10) Other nontraumatic subarachnoid hemorrhage
- I60.9 - (ICD10) Nontraumatic subarachnoid hemorrhage, unspecified
- I61.0 - (ICD10) Nontraumatic intracerebral hemorrhage in hemisphere, subcortical
- I61.1 - (ICD10) Nontraumatic intracerebral hemorrhage in hemisphere, cortical
- I61.2 - (ICD10) Nontraumatic intracerebral hemorrhage in hemisphere, unspecified
- I61.3 - (ICD10) Nontraumatic intracerebral hemorrhage in brain stem
- I61.4 - (ICD10) Nontraumatic intracerebral hemorrhage in cerebellum
- I61.5 - (ICD10) Nontraumatic intracerebral hemorrhage, intraventricular
- I61.6 - (ICD10) Nontraumatic intracerebral hemorrhage, multiple localized
- I61.8 - (ICD10) Other nontraumatic intracerebral hemorrhage
- I61.9 - (ICD10) Nontraumatic intracerebral hemorrhage, unspecified
- I62.00 - (ICD10) Nontraumatic subdural hemorrhage, unspecified
- I62.01 - (ICD10) Nontraumatic acute subdural hemorrhage
- I62.02 - (ICD10) Nontraumatic subacute subdural hemorrhage
- I62.03 - (ICD10) Nontraumatic chronic subdural hemorrhage
- I62.1 - (ICD10) Nontraumatic extradural hemorrhage
- I62.9 - (ICD10) Nontraumatic intracranial hemorrhage, unspecified
- K25.0 - (ICD10) Acute gastric ulcer with hemorrhage
- K25.2 - (ICD10) Acute gastric ulcer with both hemorrhage and perforation
- K25.4 - (ICD10) Chronic or unspecified gastric ulcer with hemorrhage

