Appendix A

1f	Active endocarditis	
Measured 180 days prior to and including day of drug initiation in any diagnosis position and inpatient or outpatient care setting:
 
Endocarditis: ICD-9 diagnosis: 421.xx , 424.9x ICD-10 diagnosis: I33.xx, I38.xx, I39.xx
	
Tan, Charlie et al. "Accuracy of administrative data for identification of patients with infective endocarditis." International journal of cardiology vol. 224 (2016): 162-164. doi:10.1016/j.ijcard.2016.09.030

2	Hemorrhage Risk-Related Criteria		
2a	Active internal bleeding	
Measured 180 days prior to and including day of drug initiation in any diagnosis position and inpatient or outpatient care setting: Refer to the 'Bleeding' sheet for detailed codes (includes GI bleeding, intracranial, intra-articular bleeding mentioned in exclusion 2b)
	
2b	
History of or condition associated with increased bleeding risk including, but not limited to:
 
 - Major surgical procedure or trauma within 30 days before the randomization visit - Clinically significant gastrointestinal bleeding within 6 months before the randomization visit - History of intracranial, intraocular, spinal, or atraumatic intra-articular bleeding - Chronic hemorrhagic disorder - Known intracranial neoplasm, arteriovenous malformation, or aneurysm 	
Measured 30 days prior to and including day of drug initiation in diagnosis position and inpatient or outpatient care setting:
 
1) Major surgery: Major surgery selected from procedure codes range 40.x- 84.x -OR-
 
2) Hemorrhagic disorder (Bleeding diathesis) 286.x Coagulation defects 287.x Purpura and other hemorrhagic conditions -OR-
 
3) Intracranial neoplasm, AV malformation, aneurysm Intracranial neoplasm ICD-9 diagnosis: 225.xx ICD-10 diagnosis: D33.xx AV malformation ICD-9 diagnosis: 747.81 ICD-10 diagnosis: Q28.2x Cerebral aneurysm: ICD-9 diagnosis: 437.3x ICD-10 diagnosis: I67.1
	
2c	Planned invasive procedure with potential for uncontrolled bleeding, including major surgery	N/A	
2d	Platelet count <90,000/ μ L at the screening visit	
Measured 30 days prior to and including day of drug initiation in any diagnosis position and inpatient or outpatient care setting:
 
Thrombocytopenia: ICD-9 diagnosis: 287.3x, 287.4x, 287.5x
	

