Appendix A

Bleeding Codes
423.0 - (ICD9) HEMOPERICARDIUM
430 - (ICD9) SUBARACHNOID HEMORRHAGE
431 - (ICD9) INTRACEREBRAL HEMORRHAGE
432.0 - (ICD9) NONTRAUMATIC EXTRADURAL HEMORRHAGE
432.1 - (ICD9) SUBDURAL HEMORRHAGE
432.9 - (ICD9) UNSPECIFIED INTRACRANIAL HEMORRHAGE
459.0 - (ICD9) HEMORRHAGE UNSPECIFIED
531.0 - (ICD9) ACUTE GASTRIC ULCER WITH HEMORRHAGE
531.00 - (ICD9) ACUTE GASTRIC ULCER WITH HEMORRHAGE WITHOUT OBSTRUCTION
531.01 - (ICD9) ACUTE GASTRIC ULCER WITH HEMORRHAGE WITH OBSTRUCTION
531.2 - (ICD9) ACUTE GASTRIC ULCER WITH HEMORRHAGE AND PERFORATION
531.20 - (ICD9) ACUTE GASTRIC ULCER WITH HEMORRHAGE AND PERFORATION WITHOUT OBSTRUCTION
531.21 - (ICD9) ACUTE GASTRIC ULCER WITH HEMORRHAGE AND PERFORATION WITH OBSTRUCTION
531.4 - (ICD9) CHRONIC OR UNSPECIFIED GASTRIC ULCER WITH HEMORRHAGE
531.40 - (ICD9) CHRONIC OR UNSPECIFIED GASTRIC ULCER WITH HEMORRHAGE WITHOUT OBSTRUCTION
531.41 - (ICD9) CHRONIC OR UNSPECIFIED GASTRIC ULCER WITH HEMORRHAGE WITH OBSTRUCTION
531.6 - (ICD9) CHRONIC OR UNSPECIFIED GASTRIC ULCER WITH HEMORRHAGE AND PERFORATION
531.60 - (ICD9) CHRONIC OR UNSPECIFIED GASTRIC ULCER WITH HEMORRHAGE AND PERFORATION WITHOUT OBSTRUCTION
531.61 - (ICD9) CHRONIC OR UNSPECIFIED GASTRIC ULCER WITH HEMORRHAGE AND PERFORATION WITH OBSTRUCTION
532.0 - (ICD9) ACUTE DUODENAL ULCER WITH HEMORRHAGE
532.00 - (ICD9) ACUTE DUODENAL ULCER WITH HEMORRHAGE WITHOUT OBSTRUCTION
532.01 - (ICD9) ACUTE DUODENAL ULCER WITH HEMORRHAGE WITH OBSTRUCTION
532.2 - (ICD9) ACUTE DUODENAL ULCER WITH HEMORRHAGE AND PERFORATION
532.20 - (ICD9) ACUTE DUODENAL ULCER WITH HEMORRHAGE AND PERFORATION WITHOUT OBSTRUCTION
532.21 - (ICD9) ACUTE DUODENAL ULCER WITH HEMORRHAGE AND PERFORATION WITH OBSTRUCTION
532.4 - (ICD9) CHRONIC OR UNSPECIFIED DUODENAL ULCER WITH HEMORRHAGE
532.40 - (ICD9) CHRONIC OR UNSPECIFIED DUODENAL ULCER WITH HEMORRHAGE WITHOUT OBSTRUCTION
532.41 - (ICD9) CHRONIC OR UNSPECIFIED DUODENAL ULCER WITH HEMORRHAGE WITH OBSTRUCTION
532.6 - (ICD9) CHRONIC OR UNSPECIFIED DUODENAL ULCER WITH HEMORRHAGE AND PERFORATION
532.60 - (ICD9) CHRONIC OR UNSPECIFIED DUODENAL ULCER WITH HEMORRHAGE AND PERFORATION WITHOUT OBSTRUCTION
532.61 - (ICD9) CHRONIC OR UNSPECIFIED DUODENAL ULCER WITH HEMORRHAGE AND PERFORATION WITH OBSTRUCTION
533.0 - (ICD9) ACUTE PEPTIC ULCER OF UNSPECIFIED SITE WITH HEMORRHAGE
533.00 - (ICD9) ACUTE PEPTIC ULCER OF UNSPECIFIED SITE WITH HEMORRHAGE WITHOUT OBSTRUCTION
533.01 - (ICD9) ACUTE PEPTIC ULCER OF UNSPECIFIED SITE WITH HEMORRHAGE WITH OBSTRUCTION

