Intracranial or retroperitoneal hemorrhage: 1 inpatient or 2 outpatient claims within 183 days; n (%)	42 (0.2%)	20 (0.1%)	0.03	72 (0.2%)	20 (0.1%)	0.03	326 (0.4%)	114 (0.3%)	0.02	440 (0.3%)	154 (0.2%)	0.02
Peptic Ulcer Disease; n (%)	3,489 (13.6%)	2,703 (18.2%)	-0.13	2,889 (8.9%)	2,207 (12.4%)	-0.11	16,513 (17.9%)	9,656 (23.8%)	-0.15	22891 (15.2%)	14566 (19.9%)	-0.12
Upper GI bleed; n (%)	0 (0.0%)	0 (0.0%)	#DIV/0!	0 (0.0%)	0 (0.0%)	#DIV/0!	86 (0.1%)	31 (0.1%)	0.00	86 (0.1%)	31 (0.0%)	0.04
Lower/unspecified GI bleed; n (%)	0 (0.0%)	0 (0.0%)	#DIV/0!	0 (0.0%)	0 (0.0%)	#DIV/0!	1,049 (1.1%)	509 (1.3%)	-0.02	1049 (0.7%)	509 (0.7%)	0.00
Urogenital bleed; n (%)	0 (0.0%)	1 (0.0%)	#DIV/0!	0 (0.0%)	0 (0.0%)	#DIV/0!	1,725 (1.9%)	729 (1.8%)	0.01	1725 (1.1%)	730 (1.0%)	0.01
Other bleeds; n (%)	4 (0.0%)	3 (0.0%)	#DIV/0!	0 (0.0%)	1 (0.0%)	#DIV/0!	969 (1.0%)	399 (1.0%)	0.00	973 (0.6%)	403 (0.6%)	0.00
Prior cancer; n (%)	2,927 (11.4%)	2,127 (14.3%)	-0.09	3,033 (9.4%)	1,750 (9.9%)	-0.02	11,109 (12.0%)	5,640 (13.9%)	-0.06	17069 (11.3%)	9517 (13.0%)	-0.05
Aspirin; n (%)	139 (0.5%)	154 (1.0%)	-0.06	357 (1.1%)	314 (1.8%)	-0.06	418 (0.5%)	266 (0.7%)	-0.03	914 (0.6%)	734 (1.0%)	-0.04

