Intracranial or retroperitoneal hemorrhage: 1 inpatient	13 (0.1%)	12 (0.1%)	0.00	15 (0.1%)	17 (0.2%)	-0.03	101 (0.3%)	99 (0.3%)	0.00	129 (0.3%)	128 (0.2%)	0.02
Peptic Ulcer Disease; n (%)	1,514 (16.9%)	1,506 (16.8%)	0.00	1,294 (11.5%)	1,278 (11.3%)	0.01	7,115 (22.9%)	7,038 (22.7%)	0.00	9923 (19.3%)	9822 (19.1%)	0.01
Upper GI bleed; n (%)	0 (0.0%)	0 (0.0%)	#DIV/0!	0 (0.0%)	0 (0.0%)	#DIV/0!	22 (0.1%)	26 (0.1%)	0.00	22 (0.2%)	26 (0.1%)	-0.04
Lower/unspecified GI bleed; n (%)	0 (0.0%)	0 (0.0%)	#DIV/0!	0 (0.0%)	0 (0.0%)	#DIV/0!	395 (1.3%)	385 (1.2%)	0.01	395 (0.8%)	385 (0.8%)	0.00
Urogenital bleed; n (%)	0 (0.0%)	1 (0.0%)	#DIV/0!	0 (0.0%)	0 (0.0%)	#DIV/0!	527 (1.7%)	533 (1.7%)	0.00	527 (1.0%)	534 (1.0%)	0.00
Other bleeds; n (%)	1 (0.0%)	1 (0.0%)	#DIV/0!	0 (0.0%)	0 (0.0%)	#DIV/0!	328 (1.1%)	314 (1.0%)	0.01	329 (0.6%)	315 (0.6%)	0.00
Prior cancer; n (%)	1,130 (12.6%)	1,119 (12.5%)	0.00	1,106 (9.8%)	1,063 (9.4%)	0.01	4,090 (13.2%)	4,060 (13.1%)	0.00	6326 (12.3%)	6242 (12.2%)	0.00
Aspirin; n (%)	68 (0.8%)	71 (0.8%)	0.00	186 (1.6%)	184 (1.6%)	0.00	201 (0.6%)	201 (0.6%)	0.00	455 (0.9%)	456 (0.9%)	0.00
Aspirin/dipyridamole; n (%)	37 (0.4%)	32 (0.4%)	0.00	79 (0.7%)	75 (0.7%)	0.00	180 (0.6%)	185 (0.6%)	0.00	296 (0.6%)	292 (0.6%)	0.00
Other antiplatelet agents; n (%)	48 (0.5%)	46 (0.5%)	0.00	62 (0.5%)	71 (0.6%)	-0.01	215 (0.7%)	224 (0.7%)	0.00	325 (0.6%)	341 (0.7%)	-0.01
PGP inhibitors; n (%)	3,868 (43.2%)	3,887 (43.4%)	0.00	5,184 (45.9%)	5,203 (46.0%)	0.00	15,745 (50.7%)	15,746 (50.7%)	0.00	24797 (48.3%)	24836 (48.4%)	0.00
Other gastroprotective agents; n (%)	81 (0.9%)	86 (1.0%)	-0.01	125 (1.1%)	122 (1.1%)	0.00	461 (1.5%)	459 (1.5%)	0.00	667 (1.3%)	667 (1.3%)	0.00
Number of lipid tests ordered												
...mean (sd)	0.66 (0.84)	0.65 (0.79)	0.01	0.29 (0.74)	0.30 (0.70)	-0.01	0.72 (0.84)	0.72 (0.84)	0.00	0.61 (0.82)	0.62 (0.80)	0.00
...median [IQR]	0.00 [0.00, 1.00]	0.00 [0.00, 1.00]	0.00	0.00 [0.00, 0.00]	0.00 [0.00, 0.00]	0.00	1.00 [0.00, 1.00]	1.00 [0.00, 1.00]	0.00	0.22 (0.94)	0.22 (0.91)	0.00
Proton pump inhibitor; n (%)	1,891 (21.1%)	1,928 (21.5%)	-0.01	2,511 (22.2%)	2,460 (21.8%)	0.01	8,637 (27.8%)	8,657 (27.9%)	0.00	13039 (25.4%)	13045 (25.4%)	0.00
H2 receptor antagonist; n (%)	406 (4.5%)	402 (4.5%)	0.00	429 (3.8%)	425 (3.8%)	0.00	2,128 (6.8%)	2,152 (6.9%)	0.00	2963 (5.8%)	2979 (5.8%)	0.00
Vitamin K therapy; n (%)	4 (0.0%)	3 (0.0%)	#DIV/0!	5 (0.0%)	4 (0.0%)	#DIV/0!	**	**	#VALUE!	#VALUE!	#VALUE!	#VALUE!
Number of neurologist visits												

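### The Bleeding code list contains no traumatic intracranial hemorrhage codes, although the trial criterion it implements bars any history of intracranial bleeding

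*Combined protocol and SAP*

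**What the plan says.** The trial criterion reproduced under exclusion 2b in Appendix A includes "History of intracranial, intraocular, spinal, or atraumatic intra-articular bleeding". The word atraumatic attaches to joint bleeding only; intracranial bleeding is barred whatever its cause. The same criterion also names trauma in the 30 days before randomization.

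The implementation column for 2a refers to the Bleeding sheet over a 180-day look-back, in any diagnosis position, inpatient or outpatient, and states that the sheet "includes GI bleeding, intracranial, intra-articular bleeding mentioned in exclusion 2b". The separate implementation of 2b codes major surgery, bleeding diathesis, and intracranial neoplasm, malformation or aneurysm. It gives no code for trauma.

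On the sheet itself (Appendix A, Bleeding Codes), all ICD-10 intracranial lines, I60 to I62, are labelled nontraumatic, from specific entries such as "I62.01 - (ICD10) Nontraumatic acute subdural hemorrhage" down to the catch-all "I62.9 - (ICD10) Nontraumatic intracranial hemorrhage, unspecified". On the ICD-9 side the label appears once, in "432.0 - (ICD9) NONTRAUMATIC EXTRADURAL HEMORRHAGE". The other intracranial lines, such as "432.1 - (ICD9) SUBDURAL HEMORRHAGE", have no qualifier.

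The unmatched table in Appendix B has a row headed "Intracranial or retroperitoneal hemorrhage: 1 inpatient or 2 outpatient claims within 183 days; n". The PS-matched table has the same row, cut short in print as "Intracranial or retroperitoneal hemorrhage: 1 inpatient".

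**The concern.** Section 5.2.2 commits the study to following the trial's criteria as nearly as the data permit. A patient with an intracranial bleed after a fall meets the trial's exclusion, but no printed code in 2a or 2b would remove that patient. Section 6.3.1 makes hemorrhagic stroke part of the primary outcome and major bleeding the control outcome, so a recent intracranial bleed is relevant to both. The appearance of intracranial or retroperitoneal hemorrhage in Table 1, after exclusion 2a has been applied, suggests that some patients of this kind pass through.

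**Working it through.** **Criterion against code list.** The criterion covers intracranial bleeding of any cause. The list covers ICD-9 430, 431, 432.0, 432.1 and 432.9 and ICD-10 I60 to I62. The ICD-9 diagnosis lines end at 719.19 and include no entry described as an injury. The omission is explicit for ICD-10. For ICD-9 it rests on the absence of any entry labelled traumatic, not on a label attached to each entry.

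**Counts in the Table 1 row (Appendix B), warfarin + rivaroxaban.**

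| Database | Unmatched | PS-matched |
|---|---|---|
| Optum | 42 + 20 = 62 | 13 + 12 = 25 |
| MarketScan | 72 + 20 = 92 | 15 + 17 = 32 |
| Medicare | 326 + 114 = 440 | 101 + 99 = 200 |
| Pooled | 440 + 154 = 594 | 129 + 128 = 257 |

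The pooled arm totals agree with the printed ones. (By coincidence, 440 is both the pooled unmatched warfarin count and the Medicare total, and 154 is both the pooled unmatched rivaroxaban count and the Optum plus MarketScan total.) As proportions, 594/223,668 = 0.27% before matching and 257/102,636 = 0.25% after.

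**Optum and MarketScan.** Before matching, 62 + 92 = 154; after matching, 25 + 32 = 57, which is 0.06% of 102,636. In both databases the hemorrhagic-stroke, upper GI-bleed and lower/unspecified GI-bleed rows are 0, so 2a appears to have removed the conditions it lists. The Table 1 row also asks for more evidence (one inpatient or two outpatient claims) than 2a, which accepts a claim in any position and setting.

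The longer window is an unlikely explanation if 183 days is the look-back and claims arrive at a constant rate. In that case 154 patients from the three extra days would imply 154 × 180/3 = 9,240 over 180 days. The flowchart in Section 5.3 shows 2a removing only 3,413 + 2,716 = 6,129 in these databases for all bleeding.

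**Medicare.** Conditions that are on the sheet remain here before matching: hemorrhagic stroke 226 + 97 = 323, upper GI bleed 86 + 31 = 117, lower/unspecified GI bleed 1,049 + 509 = 1,558. After matching the hemorrhagic-stroke count is 84 + 82 = 166. If hemorrhagic strokes also feed the composite row, they could account for up to 323 of its 440 patients before matching and 166 of 200 after.

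**Materiality.** Section 10 is reproduced with power = Φ(|ln HR| × √D / 2 − 1.96), where D is the expected number of events.

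- Stated case: D = 102,636 × 10.08/1,000 = 1,034.57. For HR 0.79: Φ(3.791 − 1.960) = 0.9665, as printed. For margin 1.46: 0.99998, as printed.
- Remove 257 patients: D = 102,379 × 10.08/1,000 = 1,031.98; superiority power 0.9661.
- Remove 257 whole pairs: D = 102,122 × 10.08/1,000 = 1,029.39; superiority power 0.9657.
- Non-inferiority power stays at 0.99998 in both cases.

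Matched prevalence is 129/51,318 against 128/51,318, a standardized difference of about 0.0004. The printed 0.02 comes from rounded percentages.

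**The case against.** A reader might infer that the 594 patients are traumatic intracranial bleeds missed by the list. The documents do not support this. The count is taken before matching, the row also includes retroperitoneal hemorrhage, its code list is not printed, and 440 of the 594 are in Medicare, where the list does not explain what remains. This part of the objection stands in full.

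Even the 154 are not proof. Other Table 1 rows also retain conditions that an exclusion should have removed: malignant hypertension in MarketScan (14,434 + 7,875, against exclusion 2e) and DVT in Optum (93 + 40) and MarketScan (90 + 33, against 3c). Definitions in Table 1 therefore differ from those of the exclusions, and a residual count does not show which codes are missing. The 183 days may describe the spacing of the two outpatient claims and not the look-back, which would undo the window calculation. The 154 could also be retroperitoneal bleeds. All this limits the table to being consistent with leakage.

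Appendix A says that full ICD-10 lists are kept in a shared folder, so the working list might hold more than the printed one. The Bleeding sheet does print its ICD-10 codes line by line, however, and nothing marks it as partial.

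Finally, Section 9 calls for the full covariate list in the propensity score, and the matched arms are level on this row. That answers a concern about confounding. It does not answer the mismatch between criterion and code list.

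**Conclusion.** The mismatch stands on the text alone: the criterion bars intracranial bleeding of any cause, the list that implements it has no entry labelled traumatic, and the trauma part of 2b is uncoded. The number of patients affected is unknown. Table 1 offers 57 matched patients in Optum and MarketScan who fit a gap in the list, with cause and look-back unproven. The further 200 in Medicare more naturally raise the question of how 2a was applied there.

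The 257 is an upper bound on what this row shows. It is not a strict bound on everyone the added codes would remove, because 2a accepts a single outpatient claim and the row does not. If the row's own list also omits traumatic codes, it counts none of these patients.

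With balanced arms and about 0.25% of the matched cohort involved, the expected effect on the hazard ratio and on power is small. The gain is in fidelity to the emulated criterion.

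**What to change.** 1. Add the traumatic intracranial hemorrhage diagnosis codes, ICD-9 and ICD-10, to the Bleeding sheet, or state why they are left out. If the shared-folder list already has them, correct the printed sheet.
2. Check how 2a was applied in Medicare, given the hemorrhagic strokes and GI bleeds that remain there.
3. Print the code list and look-back of the Table 1 variable and reconcile them with 2a. Do not simply add the composite variable to 2a: its codes are unseen, and it would bring in a retroperitoneal exclusion that the criterion does not name.
4. Rerun the Section 5.3 flowchart, the matching and balance tables, and the Section 10 power table before any comparative analysis. Section 13 is still blank in this version, so the order can be kept.

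The cost is a code-list edit, a rerun, and a repeat of the Section 10 sign-off. Judged by this row, the loss is at most about 0.25% of matched patients, or 257 pairs if whole pairs are dropped, with superiority power still about 0.966. Any correction needed in Medicare under step 2 could remove more patients and should be counted separately.

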Appendix A

K25.6 - (ICD10) Chronic or unspecified gastric ulcer with both hemorrhage and perforation
K26.0 - (ICD10) Acute duodenal ulcer with hemorrhage
K26.2 - (ICD10) Acute duodenal ulcer with both hemorrhage and perforation
K26.4 - (ICD10) Chronic or unspecified duodenal ulcer with hemorrhage
K26.6 - (ICD10) Chronic or unspecified duodenal ulcer with both hemorrhage and perforation
K27.0 - (ICD10) Acute peptic ulcer, site unspecified, with hemorrhage
K27.2 - (ICD10) Acute peptic ulcer, site unspecified, with both hemorrhage and perforation
K27.4 - (ICD10) Chronic or unspecified peptic ulcer, site unspecified, with hemorrhage
K27.6 - (ICD10) Chronic or unspecified peptic ulcer, site unspecified, with both hemorrhage and perforation
K28.0 - (ICD10) Acute gastrojejunal ulcer with hemorrhage
K28.2 - (ICD10) Acute gastrojejunal ulcer with both hemorrhage and perforation
K28.4 - (ICD10) Chronic or unspecified gastrojejunal ulcer with hemorrhage
K28.6 - (ICD10) Chronic or unspecified gastrojejunal ulcer with both hemorrhage and perforation
K55.21 - (ICD10) Angiodysplasia of colon with hemorrhage
K56.60 - (ICD10) Unspecified intestinal obstruction
K57.01 - (ICD10) Diverticulitis of small intestine with perforation and abscess with bleeding
K57.11 - (ICD10) Diverticulosis of small intestine without perforation or abscess with bleeding
K57.13 - (ICD10) Diverticulitis of small intestine without perforation or abscess with bleeding
K57.21 - (ICD10) Diverticulitis of large intestine with perforation and abscess with bleeding
K57.31 - (ICD10) Diverticulosis of large intestine without perforation or abscess with bleeding
K57.33 - (ICD10) Diverticulitis of large intestine without perforation or abscess with bleeding
K57.41 - (ICD10) Diverticulitis of both small and large intestine with perforation and abscess with bleeding
K57.51 - (ICD10) Diverticulosis of both small and large intestine without perforation or abscess with bleeding
K57.53 - (ICD10) Diverticulitis of both small and large intestine without perforation or abscess with bleeding
K57.81 - (ICD10) Diverticulitis of intestine, part unspecified, with perforation and abscess with bleeding
K57.91 - (ICD10) Diverticulosis of intestine, part unspecified, without perforation or abscess with bleeding
K57.93 - (ICD10) Diverticulitis of intestine, part unspecified, without perforation or abscess with bleeding
K62.5 - (ICD10) Hemorrhage of anus and rectum
K63.1 - (ICD10) Perforation of intestine (nontraumatic)

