5.3 Flowchart of the study cohort assembly

For rivaroxaban vs. warfarin

	Optum		Truven		Medicare	
	Less Excluded Patients	Remaining Patients	Less Excluded Patients	Remaining Patients	Less Excluded Patients	Remaining Patients
All patients		75,894,642		200,203,908		6,886,908
Did not meet cohort entry criteria	-74,960,282	934,360	-199,073,812	1,130,096	-2,028,461	4,858,447
Excluded due to insufficient enrollment	-92,301	842,059	-95,091	1,035,005	-1,551,114	3,307,333

Excluded due to prior use of referent	-482,398	359,661	-622,538	412,467	-2,080,069	1,227,264
Excluded due to prior use of exposure	-205,565	154,096	-204,425	208,042	-660,796	566,468
Excluded because patient qualified in >1 exposure category	-7	154,089	-26	208,016	-81	566,387
Excluded based on Age	-624	153,465	0	208,016	-155	566,232
Excluded based on Gender	0	153,465	0	208,016	0	566,232
Excluded based on Inclusion #1 - Age >=18	-86	153,379	-264	207,752	-65	566,167
Excluded based on Inclusion #2 & 3 - Atrial fibrillation	-83,438	69,941	-129,172	78,580	-348,521	217,646
Excluded based on Inclusion #4	-13,297	56,644	-16,046	62,534	-36,136	181,510
Excluded based on Exclusion #1a - Mitral stenosis	-275	56,369	-154	62,380	-399	181,111
Excluded based on Exclusion #1b - Prosthetic heart valve	-1,238	55,131	-789	61,591	-3,016	178,095
Excluded based on Exclusion #1e - atrial myxoma or left ventricular thrombus	-158	54,973	-35	61,556	-234	177,861
Excluded based on Exclusion #1f - Active infective endocarditis	-279	54,694	-138	61,418	-401	177,460
Excluded based on Exclusion #2a - Active bleeding or bleeding history	-3,413	51,281	-2,716	58,702	-8,256	169,204
Excluded based on Exclusion #2b.1 - Major Surgery	-1,564	49,717	-1,561	57,141	-6,484	162,720
Excluded based on Exclusion #2b.2 - Bleeding diathesis	-1,235	48,482	-885	56,256	-3,832	158,888
Excluded based on Exclusion #2b.3 - Intracranial neoplasm, AV malformation, cerebral aneurysm	-259	48,223	-283	55,973	-422	158,466
Excluded based on Exclusion #2d - Thrombocytopenia	0	48,223	0	55,973	0	158,466
Excluded based on Exclusion #2e - Uncontrolled hypertension	-47	48,176	-105	55,868	-300	158,166
Excluded based on Exclusion #3a.1 - stroke plus disabling stroke effects	-257	47,919	-152	55,716	-847	157,319
Excluded based on Exclusion # 3a.2 - stroke	-103	47,816	-88	55,628	-642	156,677
Excluded based on Exclusion #3b - TIA	-17	47,799	-25	55,603	-123	156,554
Excluded based on Exclusion #3c - DVT & PE	-1,095	46,704	-853	54,750	-3,185	153,369

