6.3.1 Outcome variables

Primary Effectiveness outcomes of interest (definitions provided in **Appendix A**):

- Primary outcome: stroke (hemorrhagic, ischemic) and systemic embolism
- Secondary outcome: Individual components
 - Hospital admission for stroke (principal diagnosis position)
 - Hospital admission for systemic embolism (principal diagnosis position)

Control outcomes of interest (control outcomes only serve to assess aspects of study validity but are not further interpreted):

1. Major bleeding

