Appendix A

533.41 - (ICD9) CHRONIC OR UNSPECIFIED PEPTIC ULCER OF UNSPECIFIED SITE WITH HEMORRHAGE WITH OBSTRUCTION
533.6 - (ICD9) CHRONIC OR UNSPECIFIED PEPTIC ULCER OF UNSPECIFIED SITE WITH HEMORRHAGE AND PERFORATION
533.60 - (ICD9) CHRONIC OR UNSPECIFIED PEPTIC ULCER OF UNSPECIFIED SITE WITH HEMORRHAGE AND PERFORATION WITHOUT OBSTRUCTION
533.61 - (ICD9) CHRONIC OR UNSPECIFIED PEPTIC ULCER OF UNSPECIFIED SITE WITH HEMORRHAGE AND PERFORATION WITH OBSTRUCTION
534.0 - (ICD9) ACUTE GASTROJEJUNAL ULCER WITH HEMORRHAGE
534.00 - (ICD9) ACUTE GASTROJEJUNAL ULCER WITH HEMORRHAGE WITHOUT OBSTRUCTION
534.01 - (ICD9) ACUTE GASTROJEJUNAL ULCER WITH HEMORRHAGE WITH OBSTRUCTION
534.2 - (ICD9) ACUTE GASTROJEJUNAL ULCER WITH HEMORRHAGE AND PERFORATION
534.20 - (ICD9) ACUTE GASTROJEJUNAL ULCER WITH HEMORRHAGE AND PERFORATION WITHOUT OBSTRUCTION
534.21 - (ICD9) ACUTE GASTROJEJUNAL ULCER WITH HEMORRHAGE AND PERFORATION WITH OBSTRUCTION
534.4 - (ICD9) CHRONIC OR UNSPECIFIED GASTROJEJUNAL ULCER WITH HEMORRHAGE
534.40 - (ICD9) CHRONIC OR UNSPECIFIED GASTROJEJUNAL ULCER WITH HEMORRHAGE WITHOUT OBSTRUCTION
534.41 - (ICD9) CHRONIC OR UNSPECIFIED GASTROJEJUNAL ULCER WITH HEMORRHAGE WITH OBSTRUCTION
534.6 - (ICD9) CHRONIC OR UNSPECIFIED GASTROJEJUNAL ULCER WITH HEMORRHAGE AND PERFORATION
534.60 - (ICD9) CHRONIC OR UNSPECIFIED GASTROJEJUNAL ULCER WITH HEMORRHAGE AND PERFORATION WITHOUT OBSTRUCTION
534.61 - (ICD9) CHRONIC OR UNSPECIFIED GASTROJEJUNAL ULCER WITH HEMORRHAGE AND PERFORATION WITH OBSTRUCTION
562.02 - (ICD9) DIVERTICULOSIS OF SMALL INTESTINE WITH HEMORRHAGE
562.03 - (ICD9) DIVERTICULITIS OF SMALL INTESTINE WITH HEMORRHAGE
562.12 - (ICD9) DIVERTICULOSIS OF COLON WITH HEMORRHAGE
562.13 - (ICD9) DIVERTICULITIS OF COLON WITH HEMORRHAGE
568.81 - (ICD9) HEMOPERITONEUM (NONTRAUMATIC)
569.3 - (ICD9) HEMORRHAGE OF RECTUM AND ANUS
569.83 - (ICD9) PERFORATION OF INTESTINE
569.85 - (ICD9) ANGIODYSPLASIA OF INTESTINE WITH HEMORRHAGE
569.86 - (ICD9) DIEULAFOY LESION (HEMORRHAGIC) OF INTESTINE
578.0 - (ICD9) HEMATEMESIS
578.1 - (ICD9) BLOOD IN STOOL
578.9 - (ICD9) HEMORRHAGE OF GASTROINTESTINAL TRACT UNSPECIFIED
719.1 - (ICD9) HEMARTHROSIS
719.10 - (ICD9) HEMARTHROSIS SITE UNSPECIFIED
719.11 - (ICD9) HERARTHROSIS INVOLVING SHOULDER REGION
719.12 - (ICD9) HEMARTHROSIS INVOLVING UPPER ARM
719.13 - (ICD9) HEMARTHROSIS INVOLVING FOREARM
719.14 - (ICD9) HEMARTHROSIS INVOLVING HAND
719.15 - (ICD9) HEMARTHROSIS INVOLVING PELVIC REGION AND THIGH

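### The code list behind exclusion 2a includes intestinal obstruction and perforation, so it can remove patients with no bleeding diagnosis, and its meaning differs between ICD-9 and ICD-10

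*Combined protocol and SAP*

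**What the plan says.** In Appendix A of the combined protocol and SAP, the trial criterion in row 2a is "Active internal bleeding". Its implementation reads: "Refer to the 'Bleeding' sheet for detailed codes (includes GI bleeding, intracranial, intra-articular bleeding mentioned in exclusion 2b". The look-back is the 180 days up to and including drug initiation. Any diagnosis position counts, from inpatient or outpatient claims, and nothing asks for a second or confirming code.

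The Bleeding Codes sheet of the same appendix includes these three entries:

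- "K56.60 - (ICD10) Unspecified intestinal obstruction"
- "K63.1 - (ICD10) Perforation of intestine (nontraumatic" (the closing bracket is cut from the quote)
- "569.83 - (ICD9) PERFORATION OF INTESTINE"

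In the flowchart of Section 5.3, patients removed by this list are counted in the row "Excluded based on Exclusion #2a - Active bleeding or bleeding history".

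**The concern.** By their own labels, the three codes describe an obstructed or perforated bowel, not a hemorrhage. One such claim in six months is enough for removal, and the flowchart then reports the patient as having bled. The emulated criterion is therefore wider than the trial criterion beside it.

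The two coding systems also do not match. Perforation appears in both. Obstruction on its own appears only under ICD-10. Cohort entry (Section 5.2.1) runs from November 4, 2011 to the end of 2017, 2018 or 2019, depending on the database, and the sheet carries both code sets. The same patient history could thus pass 2a under one system and fail it under the other. At stake are how faithfully the eligibility criterion is emulated and whether it is consistent over calendar time.

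**Working it through.** **Reading the list against itself.** The ulcer entries that name perforation also specify hemorrhage, and the diverticular entries that name it also specify bleeding. The ICD-9 entries that name obstruction as present are all ulcer codes with hemorrhage. K56.60, K63.1 and 569.83 depart from that pattern, and no rationale is given. K63.81 (Dieulafoy lesion) also lacks a bleeding word in its ICD-10 label, but its ICD-9 partner 569.86 is labelled hemorrhagic, so it is not counted here.

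| Condition | ICD-9 entry | ICD-10 entry |
|---|---|---|
| Perforation of intestine, no bleeding in label | 569.83 | K63.1 |
| Intestinal obstruction, no bleeding in label | none | K56.60 |

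Appendix A says that ICD-10 lists were produced by forward/backward mapping from ICD-9. K56.60 may have entered through the ulcer codes that combine hemorrhage with obstruction. That is an inference; the plan does not say so.

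**Reproducing the flowchart (Section 5.3).** Remaining before minus excluded should equal remaining after:

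- Optum: 54,694 − 3,413 = 51,281, as stated; 3,413 / 54,694 = 6.24%
- Truven: 61,418 − 2,716 = 58,702, as stated; 2,716 / 61,418 = 4.42%
- Medicare: 177,460 − 8,256 = 169,204, as stated; 8,256 / 177,460 = 4.65%

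Total removed: 3,413 + 2,716 + 8,256 = 14,385. Total reaching the step: 54,694 + 61,418 + 177,460 = 293,572. Share: 14,385 / 293,572 = 4.9%.

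**Size.** No count by code is given, so the number removed solely by these three codes cannot be derived; 14,385 is the ceiling. To show a range, let s be an assumed share of these exclusions due only to the three codes. The final cohort is 40,604 + 50,085 + 133,230 = 223,919.

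| s (assumed) | Patients, s × 14,385 | As % of 223,919 |
|---|---|---|
| 1% | 144 | 0.06% |
| 5% | 719 | 0.32% |
| 10% | 1,438 | 0.64% |

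For each assumed s these are upper figures, because some of these patients would fail a later criterion.

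**The case against.** The best defense concerns perforation. The sheet is said to cover items from 2b, and the trial's 2b is open-ended: it reaches conditions that raise bleeding risk beyond its listed examples. Perforation appears in both coding systems, which fits deliberate inclusion. This has some force, so the perforation codes need a justification or removal and are not plain errors. It does not rescue K56.60, which has no stand-alone ICD-9 counterpart. The mismatch between coding systems likewise rests on K56.60 alone.

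Three stronger readings are tempting, and the documents support none of them.

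- *These patients did not bleed.* A perforation or obstruction code does not show that. Some will also carry a true bleeding code and be excluded anyway. What can be said is that a bleeding diagnosis is not required.
- *The major-bleeding outcome is contaminated.* Section 6.3.1 attaches its pointer to Appendix A to the effectiveness outcomes. Major bleeding stands under a separate control heading without a pointer, and the plan says "control outcomes only serve to assess aspects of study validity but are not further interpreted". Nothing links this list to that outcome. As an illustration, suppose a share f of 5–10% of counted bleeds were unrelated events (an assumption). With diluted HR = (1 − f) × HR + f × 1, the trial benchmark of 1.04 (Section 1.4) would read 1.038–1.036, a shift of 0.002–0.004. Starting from 1.20, the upper confidence limit of that result, gives 1.19–1.18. Neither shift is large.
- *The primary result is biased.* The rule applies at baseline to both arms, and the stroke and systemic embolism codes are unaffected. No effect on the primary hazard ratio is shown.

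**Conclusion.** The point holds for exclusion 2a, as a minor defect. As written, 2a can remove patients who carry no bleeding diagnosis, and K56.60 gives it a different meaning under ICD-9 and ICD-10. K56.60 is a clear error; K63.1 and 569.83 are unexplained but possibly defensible. The number affected is unreported, cannot exceed 14,385 at this step, and is probably small.

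This rests on two assumptions: that the printed sheet is the list actually run, and that one listed code suffices, as the wording implies. Appendix A refers to an external folder for further details, which was not available for this check.

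**What to change.** 1. Count, by database, the patients excluded solely by K56.60, K63.1 or 569.83, and report the figures.
2. Delete K56.60.
3. Delete K63.1 and 569.83, or state explicitly why they qualify as bleeding-risk conditions under 2b. If they stay, relabel the flowchart row so that it no longer describes only bleeding.
4. Regenerate step 2a and everything after it: the remaining exclusions, propensity-score matching, Appendix B balance, follow-up and censoring tables, and the power tables of Section 10.
5. If the list is also used for the major-bleeding control outcome, use the corrected list there. The plan should say which list defines that outcome.

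The edit is small, but the rerun is not trivial. The balance and power material carries review dates of 9/8/20 and 9/29/20, so the regenerated tables would need review again. The date in Section 13 is blank, so in this version the correction can still precede the comparative analysis.
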